The biliopancreatic limb length may explain the results of superior excess weight reduction as well as the higher incidence of hemoglobin deficiency after 5 year follow-up comparing MGB vs RYGB (7). This malabsorption could result in severe malnutrition defined as a %EBMIL > 100 % and an albumin level < 30 g/l (8).

In 2005 Rutledge observed malnutrition in 31/2,401 patients (5), Noun et al. reported 4 cases of malnutrition out of 1,000 patients of MGB (9), Lee et al.

(10) reported a revision rate of 1.7% at 9 years follow-up in their series of 1,322 patients and the most common cause of revision was malnutrition in nine cases. In addition, Wang et al. (11) operated 423 MGB and reported anemia as a late complication in 28% of patients, and most cases were microcytic, the reason for the high incidence was reported to be likely due to the duodenal bypass with malabsorption of iron. However all data published on the mal-absorptive effects of MGB are retrospective so, until now, there is no prospective comparative study to assess the malabsorptive efficacy of MGB vs RYGB. Recently an experimental study carried out in a rat model evaluated the malabsorption of MGB versus RYGB suggesting a higher protein malabsorption induced by MGB (not compensated by the intestinal adaptation) than RYGB (12).

Recent works have indicated that the gut microbiota may mediate some of the beneficial effects of bariatric surgery, and changes in the composition and diversity of the gut microbiota have been observed in the short and long term after RYGB in humans (13, 14), as well as after vertical sleeve gastrectomy and RYGB in mice (15). However, there are no investigations of these changes after MGB.

AIM OF WORK:

To evaluate in patient undergoing MGB or RYGB the effect of the treatment on enteric mal-absorption and microbiota profile in the first year after surgery.

Primary end point:

-To evaluate and compare RYGB vs MGB bile acids levels and microbiota profile shift at 6 and 12 months after surgery and its impact on metabolic and nutritional status after surgery.

Secondary end point:

-To measure GLP-1 plasma level (pg/mL) before and 12 months after surgery in MGB vs RYGB patients.

Other parameters:

1. To evaluate at 0 – 6 and 12 months after surgery the enteric mal-absorption profile in terms of lipid (Triglycerides, cholesterol, HDL and LDL), proteins (hemoglobin, albumin and ferritin), carbohydrates and micronutrients (minerals and vitamins) and nutritional status in subjects undergoing MGB vs RYGB.
2. To compare the effect of RYGB vs MGB surgery on total weight loss percent, excess weight loss percent (%EWL), excess BMI loss percent, major co-morbidities control and quality of life.
3. To evaluate the endoscopic /histological esophageal mucosal lesions secondary to bile reflux at 12 months in MGB vs RYGB patients
4. to evaluate energy expenditure at 0 and 12 months by Indirect calorimetry

Type of study:

Multicentric Prospective pilot comparative study.

Patients:

We had to evaluate Sample Size using bariatric patients population who underwent MGB or RYGB during 12 months (the follow up period of this study) in the three centres involved in the study, because of there aren't others high methodological level studies or randomized trials or methnalysis about this argument (Primary end points and secondary and points). Our population is 285 patients: to obtain a confidence level of 95 %, an effect size of 0.5, Sample size is 90 patients (45 MGB and 45 RYGB) with an interval confidence of 8.56.

Determine Sample Size

Confidence Level: 95% 99%

Confidence Interval:

Population:

Sample size needed:

Find Confidence Interval

Confidence Level: 95% 99%

Sample Size:

Population:

Percentage:

Confidence Interval:

Tab 1

Tab 2

The sample size will be 90 cases (45 MGB and 45 RYGB) considering at least 20% drop-out at 1 year. (Tab 1-2)

Inclusion Criteria:

Obese patients with age 18-65 years old, BMI 40-55 kg/m², non smokers, and candidates to primary MGB or RYGB without any concomitant surgeries except

hiatal hernia repair. Patients will be informed on the differences of the two procedures and the enrollment in the two study groups will be on the basis of patient choice.

Exclusion Criteria:

- Age ≤ 18 or ≥ 65 years old,
- BMI ≤ 40 or ≥ 55
- Smokers
- Any required associated surgical procedure except hiatal hernia repair
- Conversion to open surgery
- Postoperative complications requiring reoperation
- No compliance to the follow up schedule.
- Histological positivity to *Helicobacter pylori* previous or current
- Patients with different intraoperative measurement of the bowel distal to Treitz Ligament (tolerance plus or minus 10%).
- Free PPI 4 weeks before 6th month (after surgery)
- Corticosteroids, vitamin E, fish oil treatment in the previous two months
- Anti or pre- biotics treatment in the previous 2 months
- Chronic gastrointestinal diseases or syndromes (e.g., IBD, IBS)
- Previous bariatric surgery (intra-gastric balloon excluded).
- Previous resective bowel surgery

- Previous pancreatic surgery
- Previous hepato bilio pancreatic surgery
- Gallbladder gallstones

Methods:

Pre-and post-operative Assessment:

All patients will sign an informed consent (Sicob guidelines 2016). Study protocol will be approved by the Ethical Committee.

All patients will undergo routine blood laboratory investigations before surgery, 6 months and 12 months after surgery including: serum hemoglobin, glucose, HbA1c, cholesterol, triglycerides, LDL, HDL, T3, T4, TSH, GLP-1. Assessment of the nutritional status will be performed before 6- and 12 months after bariatric surgery by blood testing for serum iron, calcium, zinc and vitamins A, D, B12 and cortisol level.

A standardized meal test will be performed before, 6 and 12 months after bariatric surgery with 250 ml of liquid meal Oxepa®, (375 calories, 55.5% fat,

28% carbohydrate, 16.5% protein). Blood samples will be collected at baseline, 30, 60, 90 and 120 minutes after meal test in order to assess the concentration of the circulating lipids, GLP-1, bile acids (C4 precursor of bile acids) and FGF 19 (Fibroblast Growth Factor 19) levels. A stool sample will be collected at 0 – 6 – 12 months (It' s necessary to indicate date and time of defecation) stored at - 80°C for targeted gut microbiota metagenomic (MG) study, lipids and proteins levels assessment. Every sample will be made by two parts: one for metagenomics evaluation and the other one for lipids and proteins levels assessment. Before fecal sampling, patients will be asked to fill out a three days food diary. All patients with vitamin D deficiency (< 20 ng/mL) will be supplemented before surgery with 10,000 IU of Vitamin D daily (16). Every value of nutritional status should be annotated in Winfood software. The selection criteria, work up, informed consent and schedule of the multidisciplinary follow up will follow the Guidelines of Italian Society for Obesity Surgery (SICOB) adopted in September 2016 (www.sicob.org).

Intra-operatively:

Standardization of the techniques will be guaranteed:

1. RYGB group
2. MGB group

All patients will have intraoperative measurement of the whole length of bowel from Treitz ligament to the ileocecal junction (expected range 6-8 m). The common limb will be therefore about 2/3 of total small bowel length.

Roux en Y gastric bypass

The steps of the standard double loop RYGB technique will be followed (17). The gastric pouch will be created 7 cm from the gastro-esophageal junction to obtain a volume of 30-40 ml, and the length of the alimentary limb will be 150 cm and 3.5-4 cm gastro-jejunostomy will be performed by linear stapler. The length of the biliopancreatic limb will be from 65 to 75 cm beyond the ligament of Treitz. The lengths of both limbs should carefully measured with a graduated instrument. The mesenteric defects will be closed.

Mini-gastric Bypass

The gastric pouch will be performed starting below the incisura angularis (transverse resection 4 cm) on the lesser curvature (18). Then the stomach will be transected against a 36 Fr bougie up to the gastro-esophageal junction. Then 1/3 of the small bowel will be excluded (approximately 200cms) and 3.5-4 cm gastro-jejunostomy will be performed by linear stapler.

Postoperative diet

After surgery and under the supervision of the registered dietitian, the diet will be transitioned from liquid diet for 2 weeks to pureed proteic diet for 1 week then soft solid proteic diet for 2 weeks then maintenance (regular food). All patients should have daily vitamin and mineral supplementation up one year after surgery following the chart below:

Vitamin A	0,8 mg
Vitamin B	11,65 mg
Vitamin B	22,1 mg
Vitamin B	324 mg
Vitamin B	62,1 mg
Vitamin B12	0,00375 mg
Vitamin C	120 mg
Vitamin D3	0,0075 mg
Vitamin E	12 mg
Vitamin K1	0,0375 mg
Folic Acid	0,2 mg
Pantothenic Acid	9 mg
Iron	21 mg
Magnesium	187,5 mg
Selenium	0,055 mg
Zinc	10 mg

Diet progression after bariatric surgery

1. Liquid Proteic Diet (for 2 weeks)

Types of food	Calories/day
Reduced fat milk Lactose-free: 200ml	Protein: 52.32g (31.29%)

Fruit juice: 200ml	Fat: 14.52g (19.54%)
Light white yogurt: 125ml	Carbohydrate: 86.6g (51.58%)
Vegetable clear broth: 400ml	Kcal: 669
Oral protein supplementation: 400ml	

2. Pureed Proteic Diet (for 1 week)

Types of food	Calories/day
Reduced fat milk Lactose-free: 200ml	Protein: 62.4g (25.69%)
Light white yogurt: 125ml	Fat: 43.26g (40.07%)
Vegetable clear broth: 400ml	Carbohydrate: 85.52g (35.21%)
Oral protein supplementation: 400ml	Kcal: 971.65
Pureed lean beef, chicken or turkey, fish (or baby food meats): 80g	
Pureed fruits (or baby food fruit): 100g	
Soft cheese: 50g	
Extra virgin oil: 10g	

3. Soft Solid Proteic Diet (for 2 weeks)

Types of food	Calories/day

Reduced fat milk Lactose-free: 200ml
 
Light white yogurt: 125ml
 
Oral protein supplementation: 400ml
 
Chopped lean meats (or Lean ground beef or turkey, or Deli-sliced turkey, breast, chicken, ham): 50g
 
Tuna fish, salmon or white fish: 50g
 
Pureed fruits (or baby food fruit) or canned fruits: 100g
 
Mashed or well-cooked vegetables: 100g
 
Extra virgin oil: 10g
	
Protein: 74.4g (30.41%)
 
Fat: 32.66g (30.04%)
 
Carbohydrate: 99.4g (40.60%)
 
Kcal: 978.65

4. Maintenance (Regular Food)

Types of food	Calories/day
---------------	--------------

Reduced fat milk Lactose-free: 200ml	Protein 78.9gm (27.69%)
Biscuits: 30g	Fat 42.24gm (33.35%)
Oral protein supplementation: 200ml	Carbohydrate: 116.6 gm
Light white yogurt: 125ml	(40.9%)
Lean red meat (or tender chicken, turkey and beef: 70g	Kcal 1116.64
Fish: 70g	
Raw fruits without skins: 100g	
Raw and cooked vegetables: 100g	
Toasted breads or Low fat crackers: 30g	
Extra virgin oil: 20g	

Postoperative follow up:

Total weight loss percent, excess weight loss percent (%EWL), excess BMI loss percent, co-morbidities control and quality of life, evaluated by The TSD-OC (SIO obesity-related disability) test (19). It is a questionnaire developed by the Italian Society of Obesity (SIO); it is made of 36 items divided into 7 sections: pain, rigidity, activities of daily living, housework, outdoor activities, occupational activities, and social life. Each question is answered using a visual

analogue scale, with a score ranging from 0 (absence of difficulty) to 10 (the highest degree of disability) for each item.

Data recording and variables analysis:

Basic demographic data are recorded as well as detailed information on history, preoperative data, surgical procedure, intra-operative findings, and postoperative course. The statistical analysis will be performed on the pooled groups. All statistical analyses will be performed using IBM SPSS v.20 software. P value of less than 0.05 will be considered statistically significant.

References

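### The two excess-loss weight measures depend arithmetically on starting BMI, so with patient-chosen surgery the weight comparison needs a lead measure and adjustment for baseline BMI

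*Protocol*

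**What the plan says.** Under Other parameters, item 2, the protocol sets out to compare RYGB with MGB on "total weight loss percent, excess weight loss percent (%EWL), excess BMI loss percent, major co-morbidities control and quality of life". The section on postoperative follow-up lists the same three weight measures. Neither place says which of them leads, and neither gives an ideal weight or reference BMI.

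The Inclusion Criteria admit "Obese patients with age 18-65 years old, BMI 40-55 kg/m², non smokers". They also state that "the enrollment in the two study groups will be on the basis of patient choice". No matching or stratification on BMI is described.

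The section on data recording and variables analysis says that preoperative data are recorded and that "P value of less than 0.05 will be considered statistically significant".

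**The concern.** Excess weight loss and excess BMI loss divide the loss by the excess over a reference value. A lighter patient has a smaller excess, so the same relative loss scores higher. Arms formed by patient choice can differ in mean starting BMI. An unadjusted comparison on either measure then mixes the effect of the procedure with the starting BMI of those who chose it.

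At stake is the reading of the weight result. The arm that starts lighter could look better on two of three measures at equal relative loss, and the protocol does not say which measure prevails if they disagree. Agreement between the two excess-loss measures could also be taken for corroboration when they may be the same quantity.

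**Working it through.** **The plan's own figures.** The protocol states no figure for the weight outcomes. Its one computed figure, the interval of 8.56 for 90 patients out of 285, reproduces as 100 × 1.96 × √(0.25/90) × √(195/284) = 8.56. It is a survey precision and does not bear on this point.

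**Inputs.** From the protocol: BMI 40-55, 45 patients per arm, at least 20% drop-out (45 × 0.8 = 36 per arm), threshold p < 0.05. Assumed: reference BMI 25 (range 22-25), total weight loss (TWL) of 30%, and a two-sided test, since sidedness is not stated.

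**Identity.** Height is fixed, so weight can be written as BMI. With starting BMI B and reference R:

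- loss in BMI units = TWL% × B / 100
- excess = B − R
- excess BMI loss % = TWL% × B / (B − R)

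Excess weight loss % has the same formula when ideal weight is set at BMI R. With a common R the two measures are therefore identical.

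**Size for a gap in starting BMI, at 30% TWL in both arms.**

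- 1 unit, R = 25: 30 × 44.5/19.5 = 68.5 and 30 × 45.5/20.5 = 66.6; gap 1.9 points.
- 2 units, R = 25: 30 × 44/19 = 69.5 and 30 × 46/21 = 65.7; gap 3.8 points.
- 2 units, R = 22: 30 × 44/22 = 60.0 and 30 × 46/24 = 57.5; gap 2.5 points.

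The direction is the same for any reference in this range; the size depends on it.

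**How often this would reach p < 0.05.** Simulation with 4,000 replicates per setting, a t-test, 45 or 36 per arm, true mean TWL 30% in both arms, SD of TWL 5 to 9, baseline BMI truncated normal within 40-55 (SD 3.5 before truncation), R = 25. The distributional values are assumptions.

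| Mean BMI gap | Gap in excess loss (points) | Rejections on excess loss |
|---|---|---|
| 0 | about 0 | 4.7-5.4% |
| about 0.8 | 1.3-1.4 | 5.5-7.4% |
| about 1.6 | 2.6-2.7 | 7.9-17.3% |
| about 2.3 | 3.9-4.0 | 12.4-32.3% |
| about 3.1 | 5.1-5.3 | 19.4-52.0% |

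On TWL the rejection rate stayed at 4.3-5.6% throughout, as it must, because TWL was generated independently of BMI.

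**The same check from the other side.** Suppose instead that true excess loss is 67.5% in everyone, with R = 25. Then TWL = 67.5 × (B − 25)/B:

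- 2 units: 67.5 × 19/44 = 29.1 and 67.5 × 21/46 = 30.8; gap 1.7 points.
- 4 units: 67.5 × 18/43 = 28.3 and 67.5 × 22/47 = 31.6; gap 3.3 points.

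Now TWL shows the difference and excess loss does not. At one and the same starting BMI, however, the two scales differ only by the constant B/(B − R). Equality on one is then equality on the other, which is why all three comparisons need the adjustment.

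**The case against.** **Peripheral outcomes.** They rank below the primary (bile acids and microbiota) and secondary (GLP-1) endpoints of a pilot study, and no sample size rests on them. This stands and sets the severity.

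**TWL is already listed, and first.** A discordant excess-loss result would be visible beside it. This stands in part: the reader could see the conflict but would have no stated rule for resolving it.

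**Reference BMI and adjustment are SAP matters.** The SAP is not shown, and nothing in the protocol precludes adjustment. So neither gap is an error in itself. What remains is a choice the protocol makes: three measures for one comparison, two of them tied to starting BMI, in arms that patients select.

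**No scale is neutral.** A reader might infer that TWL is the unbiased measure and the excess-loss measures the biased ones. The documents do not support that; the reverse calculation shows that it assumes relative loss is constant across BMI.

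**The excess-loss scale belongs to the rationale.** The background describes MGB's advantage over RYGB in terms of excess weight and uses excess BMI loss in its definition of severe malnutrition. A reader might conclude that these measures should support no between-procedure statement at all. That goes too far; adjusting them for baseline BMI is enough.

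**Conclusion.** The point holds at low severity. The dependence on starting BMI is an identity. Whether it distorts this trial depends on how far the arms differ in baseline BMI, and the protocol gives no figure for that. With reference BMI 25 and 30% TWL, a gap of 2 units produces 3.8 points, and below about 1 unit the effect is under 2 points with rejection rates close to nominal.

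Two larger figures are tempting. A gap of 4 units (BMI 43 against 47) gives 71.7% against 64.1%, or 7.6 points, but nothing in the protocol suggests so large a gap between arm means. Across the entry range, excess loss runs from 80% at BMI 40 to 55% at BMI 55. That is a contrast between individual patients at limits which the exclusion list itself rules out, and not an expected difference between arms.

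That the two excess-loss measures are one number rests on a common reference BMI, which the protocol does not state.

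**What to change.** In item 2:

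- Name 12-month total weight loss percent as the lead weight measure. The reason is to have one lead fixed in advance, not that this scale is free of assumptions.
- Adjust every between-procedure weight comparison (total weight loss, excess weight loss and excess BMI loss) for baseline BMI.
- Report the two excess-loss measures as supportive, with one reference BMI common to the three centres, and say that with a shared reference they are the same quantity.

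The form of the BMI term can be left to the SAP. The relation is curved (80.0, 67.5, 60.0 and 55.0 at BMI 40, 45, 50 and 55 for 30% TWL and reference 25), so a straight line is only an approximation.

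The cost is wording. BMI is already needed for eligibility, and all three measures come from the same weights and heights. The downside is that two familiar measures become supportive. The change deals only with dependence on starting BMI; other differences between patients who choose one procedure or the other can still bias all three measures.

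### Oesophageal lesions attributed to bile reflux are compared between self-selected arms at 12 months with no baseline assessment specified, so pre-existing lesions could be counted as procedure effects

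*Protocol*

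**What the plan says.** The protocol's list headed Other parameters includes, as item 3: "To evaluate the endoscopic /histological esophageal mucosal lesions secondary to bile reflux at 12 months in MGB vs RYGB patients". Only the 12-month time point is given.

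Other items with stated times do name a pre-operative measurement:
- Item 1: "To evaluate at 0 – 6 and 12 months after surgery the enteric mal-absorption profile".
- Item 4: "to evaluate energy expenditure at 0 and 12 months by Indirect calorimetry".
- Secondary end point: "To measure GLP-1 plasma level (pg/mL) before and 12 months after surgery in MGB vs RYGB patients".

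The Methods section on pre- and post-operative assessment describes blood tests, a meal test, stool samples and a food diary. It describes no endoscopy or oesophageal biopsy at any time, no lesion grading, and no rule for deciding that a lesion is due to bile reflux.

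Four further statements bear on the point:
- Allocation (Inclusion Criteria): "the enrollment in the two study groups will be on the basis of patient choice". Patients are first told how the procedures differ.
- An exclusion criterion: "Any required associated surgical procedure except hiatal hernia repair". Patients having a hiatal hernia repaired can therefore enter.
- Another exclusion criterion: "Histological positivity to *Helicobacter pylori* previous or current".
- Work-up (Methods): "The selection criteria, work up, informed consent and schedule of the multidisciplinary follow up will follow the Guidelines of Italian Society for Obesity Surgery". The content of that guideline is not reproduced.

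**The concern.** A lesion seen once, a year after surgery, may be new or may have been there before. Without a pre-operative finding the two cannot be told apart, and this raises two separate problems.

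**Attribution.** Ascribing a lesion to bile reflux after the operation requires at least that it arose or worsened afterwards. This fails even if the arms are perfectly balanced.

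**Confounding.** There is no randomisation to balance pre-existing lesions. Patients choose after being told the differences between the procedures, and those with hiatal hernia or reflux disease are not excluded by name. If reflux history influences the choice, the 12-month difference mixes that imbalance with the effect of surgery, in either direction.

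The timing of data collection is fixed in the protocol. A statistical analysis plan cannot adjust for a baseline that was never recorded.

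**Working it through.** **The plan's own figures.** The protocol gives no figure for this parameter. Its one computed figure, an interval of 8.56 for 90 patients out of a population of 285, is the 95% half-width for a single proportion of 0.5 with finite-population correction: 1.96 × √(0.25/90) × √((285 − 90)/(285 − 1)) = 0.0856. It reproduces, but has no bearing on a between-arm comparison of lesions.

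**Inputs from the protocol.** 45 patients per arm; drop-out of at least 20% at one year, so 45 × 0.8 = 36 per arm if drop-out is exactly 20% and equal in both arms; significance level 0.05, taken here as two-sided.

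**Assumed inputs.** All lesion prevalences, persistence and incidence below are assumptions.

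**How a baseline imbalance carries through.** Let b be the pre-operative prevalence in an arm, s the share of those lesions still present at 12 months, and i the incidence among patients free of lesions at baseline, with s and i equal in both arms (no procedure effect). Then

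12-month prevalence = b·s + (1 − b)·i = i + b·(s − i),

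so the spurious difference = (b₁ − b₂)·(s − i). With full persistence and no new lesions (s = 1, i = 0) the whole baseline imbalance is carried over. With i = 0.05, a 20-point imbalance becomes 0.20 × 0.95 = 0.19.

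**False-positive rate, s = 1 and i = 0.** For the two-sided pooled two-proportion test with n per arm and mean prevalence p̄ = 0.20:
- Standard error under the null: SE₀ = √(2·p̄(1 − p̄)/n), which is 0.0843 for n = 45 and 0.0943 for n = 36.
- Observed difference needed for p < 0.05: 1.96 × SE₀ = 0.165 (n = 45) or 0.185 (n = 36).
- Rejection probability: Φ((d − 1.96·SE₀)/SE₁) + Φ((−d − 1.96·SE₀)/SE₁), where SE₁ = √(p₁(1 − p₁)/n + p₂(1 − p₂)/n).

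Example, 25% vs 15% with n = 45: SE₁ = 0.0837 and (0.10 − 0.165)/0.0837 = −0.78, so the rate is 0.218.

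| Assumed pre-existing prevalence | Spurious difference | 45 per arm | 36 per arm |
|---|---|---|---|
| 20% vs 20% | 0 points | 5% | 5% |
| 21.25% vs 18.75% | 2.5 points | 6% | 6% |
| 22.5% vs 17.5% | 5 points | 9% | 8% |
| 25% vs 15% | 10 points | 22% | 18% |
| 30% vs 10% | 20 points | 67% | 57% |

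**Attribution with balanced arms.** With 20% pre-existing lesions in both arms, full persistence, and new lesions in 5% or 10% of the remaining 80%, the share of 12-month lesions that predate surgery is 0.20/(0.20 + 0.80 × 0.05) = 83%, or 0.20/(0.20 + 0.80 × 0.10) = 71%. This needs no imbalance.

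**The case against.** **An objective line need not list every visit.** The primary end point also names only 6 and 12 months, yet Methods supplies its baseline through stool samples and meal tests before surgery. That is fair, and the contrast with items 1 and 4 proves little by itself. But for the oesophagus Methods supplies nothing. What stands is that no baseline is specified; that none will exist in practice does not follow.

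**A pre-operative endoscopy probably takes place.** The *H. pylori* criterion, the deferral to the national guideline and the general statement that pre-operative data are recorded all point that way. A reader might go further and infer that every patient has a usable baseline endoscopy. The text does not support this: the criterion covers previous as well as current positivity, so the histology may be historical. Gastric histology also supplies no oesophageal biopsy, and nothing links any such examination to item 3.

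**Pre-existing lesions need not be counted.** Some heal by 12 months, and the item is limited to lesions due to bile reflux. So they could be counted, not would be. The limitation protects little, since no attribution criterion is given.

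**Imbalance is conjecture.** This is correct. Hiatal hernia repair is allowed in both arms and no figure in the protocol suggests a difference. Equally, nothing in the design prevents one.

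**Conclusion.** The point holds in a limited form. As written, item 3 cannot separate lesions present before surgery from lesions that followed it, and the comparison is open to confounding by patient choice. The size is unknown. The illustrative false-positive rates of about 18-22% and 57-67% rest on assumed imbalances of 10 and 20 points, full persistence and no new lesions; new lesions at equal incidence in both arms, or healing, would reduce the spurious difference. A reader might infer that any plausible imbalance would create or hide a difference. The table does not support that: at 2.5 points the rate is about 6% against the nominal 5%.

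A reader might also take this for the main safety question about MGB. The protocol does not say so. Its aim and primary end point concern malabsorption, bile acids and microbiota, and this is the third of four other parameters in a pilot study. The severity is modest. It is still worth correcting, because a baseline not recorded before surgery cannot be recovered later.

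**What to change.** 1. Where a pre-operative endoscopy is done, record its oesophageal findings with the same grading as at 12 months.
2. Make new or worsened endoscopic lesions from baseline to 12 months the compared outcome, taking account of baseline status. The form of the model can be left to the analysis plan.
3. For the histological part, and for any patient without a baseline examination, report 12-month prevalence only, label it descriptive, and drop the attribution to bile reflux.

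No extra endoscopy or biopsy is requested. The cost is one more recorded field, slightly more analysis, and a weaker statement for the histological part. Patients without a baseline examination also drop out of the main comparison of endoscopic lesions, so their number should be reported by arm.

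### The 90-patient sample size is a one-sample survey margin of error, so it does not support the stated effect size of 0.5 for MGB versus RYGB

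*Protocol*

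**What the plan says.** The sample-size paragraph is in the Patients section of the protocol. It starts from the bypass caseload of the three centres over 12 months ("Our population is 285 patients") and continues "to obtain a confidence level of 95 %, an effect size of 0.5, Sample size is 90 patients (45 MGB and 45 RYGB". To this it attaches a precision figure of 8.56, which it calls an interval. Below it are the field labels of an online calculator. The block labelled "Find Confidence Interval" asks for a confidence level, a sample size, a population and a percentage. The paragraph ends: "The sample size will be 90 cases (45 MGB and 45 RYGB) considering at least 20% drop-out at 1 year".

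The primary end point is comparative: "To evaluate and compare RYGB vs MGB bile acids levels and microbiota profile shift at 6 and 12 months after surgery". Allocation is not randomised: "the enrollment in the two study groups will be on the basis of patient choice". The data-recording section calls P below 0.05 statistically significant. The sample-size paragraph names no outcome, standard deviation, between-group difference or power.

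**The concern.** The calculator fields are those of a survey tool, which returns the precision of one percentage estimated in one sample from a finite population. The trial compares two groups of 45 on bile acids and microbiota. If 90 and 8.56 come from the survey formula, they describe nothing that the study will estimate, and "an effect size of 0.5" is a wrong label for the percentage input.

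A reader of the protocol would take the study to be sized, at 95% confidence, for an effect of 0.5 between the operations. If it then found no significant difference, the result could be over-read as evidence that MGB and RYGB do not differ, when the study had little more than an even chance of detecting an effect of that size.

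**Working it through.** **Inputs from the protocol.** Confidence level 95% (z = 1.96); population N = 285; sample n = 90 (45 + 45); the value 0.5; interval 8.56; drop-out at least 20%; significance level 0.05.

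**Assumed, because not stated.** Two-sided testing; for the two-group figures, 0.5 read as a standardised mean difference; 80% power as the reference level.

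**1. Reproducing the protocol's figure.** The margin of error for one proportion with finite-population correction is

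e = 1.96 × √[p(1 − p)/n] × √[(N − n)/(N − 1)]

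With p = 0.5, n = 90 and N = 285:

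e = 1.96 × √(0.25/90) × √(195/284) = 0.0856, or 8.56 percentage points.

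This matches to two decimals. The inverse agrees: n₀ = 1.96² × 0.25/0.0856² = 131.07, and 131.07/(1 + 130.07/285) = 90.0. Other inputs do not fit: without the finite-population factor the margin is 10.33; with p = 0.45 it is 8.52; with p = 0.40 it is 8.39. So 0.5 is the percentage field.

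**2. Could 90 come from a two-group calculation instead?** At a standardised difference of 0.5 and alpha 0.05, by the normal approximation and before any drop-out allowance:

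| Test | Power | Total n |
|---|---|---|
| One-sided | 80% | 100 |
| Two-sided | 80% | 126 |
| One-sided | 90% | 138 |
| Two-sided | 90% | 170 |

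None of these gives 90.

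**3. Drop-out.** 90 × 0.8 = 72 evaluable. The protocol's own formula with n = 72 gives 1.96 × √(0.25/72) × √(213/284) = 10.0 points. Without the finite-population factor the margins are 10.3 (n = 90) and 11.5 (n = 72).

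**4. What the design delivers for a between-group difference.** Two-sided 5% t-test, equal arms, one unadjusted continuous outcome. The 95% CI half-width is t × √(2/n) in SD units:

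- n = 45: 1.987 × √(2/45) = 0.42
- n = 36: 1.994 × √(2/36) = 0.47

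Power and detectable difference are from the noncentral t distribution:

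| | 45 per arm | 36 per arm |
|---|---|---|
| Power at 0.5 SD | 65% | 55% |
| Difference detectable with 80% power | 0.60 SD | 0.67 SD |
| 95% CI half-width | 0.42 SD | 0.47 SD |

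For 80% power at 0.5 SD the same test needs 63.8, so 64 evaluable patients per arm. A one-sided test would need 51 per arm, still above 45.

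**The case against.** - **The arithmetic is correct.** This is true: 90 and 8.56 reproduce exactly. The defect is a method that does not fit the comparison, together with a mislabelled input.
- **If 0.5 is only a percentage, the protocol never planned for a standardised difference of 0.5, so there is no target that it misses.** This limits how the power figures may be used. They show what follows if the printed label is taken at face value; they are not a failure against a stated power. The mislabelling remains.
- **A simple t-test is a simplification.** This stands. A microbiota profile is multivariate and the meal test has repeated samples. Baseline adjustment could raise power, and adjustment for confounding under patient choice could lower it. The figures are an approximation for one unadjusted outcome.
- **Drop-out may already be inside the 90.** This is plausible. The same formula for a 10-point margin in 285 gives n₀ = 1.96² × 0.25/0.10² = 96.04 and n = 96.04/(1 + 95.04/285) = 72.02, and 72/0.8 = 90. The calculator's field values are not legible in the text at hand, so this cannot be settled. What remains is narrower: 8.56 is the precision of the enrolled number, not of the number expected to be analysed.
- **The 285 may mean an annual caseload rather than patients already operated on.** The wording allows both. Under either reading the finite-population factor is inappropriate, because the aim is to compare two operations, not to describe those 285 patients.
- **It is a pilot.** A pilot needs no formal power calculation, and no more patients are asked for here. But the protocol makes a specific quantitative claim and also sets a P < 0.05 criterion; pilot status does not make the claim correct.

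**Conclusion.** The concern holds. The only sample-size justification in the protocol is the margin of error of one pooled proportion in a finite population of 285. It sizes no difference between MGB and RYGB, and the 0.5 is not an effect size. A statistical analysis plan, if one exists, would not cure this, because the wrong statement is in the protocol itself.

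Read at face value, the stated effect would be detected with 65% power if all 90 patients were evaluable and with 55% power if 72 were. The confidence interval for the difference would extend 0.47 SD either side of the estimate at 36 per arm. These sizes rest on the assumptions in the working and are on the favourable side in two respects: drop-out is given as at least 20%, and completers may not divide equally. That 8.56 is a one-sample survey margin depends on none of these assumptions.

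**What to change.** Keep 90 patients. Delete the reasoning from the population of 285, the effect size of 0.5 and the 8.56 interval, together with the calculator fields, and replace them with a statement such as:

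> Ninety patients will be enrolled (45 per arm). With 20% drop-out, 72 are expected to be evaluable (36 per arm). For one continuous outcome compared without adjustment between equal arms, the 95% confidence interval for the difference will have a half-width of about 0.47 SD. A two-sided 5% test will have 80% power for a standardised difference of 0.67 and 55% power for 0.5. As this is a pilot study, estimates will be reported with confidence intervals. Higher drop-out or unequal arms would reduce this precision.

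The cost is one reworded paragraph, with no added patients or procedures. The stated performance becomes less favourable, but it then describes the comparison that the trial makes.
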